15 REFERENCES10

APPENDIX A: SCHEDULE OF ASSESSMENTS12

1 PROTOCOL SYNOPSIS

Title	A Post-Market, Single Blind, Randomized Clinical Prospective Study on Intradialytic Symptoms in Subjects treated with Qd 500 vs Qd 300
Study Goal	To determine the impact of dialysate flow rate (Qd) on Subject reported dialysis related symptoms and on time to recovery post dialysis.
Study Background	Subjects undergoing conventional intermittent thrice weekly hemodialysis using a Qd of 500ml/min or higher report many inter and intra dialytic symptoms. Common symptoms include fatigue, cramping, and insomnia. Subjects treated on the Tablo hemodialysis system report 'feeling better'. Tablo has a dialysate flow rate of 300 ml/min.
Study Objective	The objective of this study is to determine if Subjects who report dialysis symptoms while meeting adequacy (as determined by Kt/V of 1.2 or greater) on thrice weekly dialysis or who have a recovery time of at least 4 hours when treated on a conventional, i.e. non Tablo, hemodialysis device feel better with a reduced dialysate flow rate of 300ml/min based on an assessment of time to recovery post dialysis and Subject reported symptoms via a modified weekly ESAS survey.
Study Length	The study will last approximately 8 weeks consisting of chart review, Subject selection, medical record review, data collection and data analysis.
Inclusion Criteria	
 1. Subject has provided informed consent and has signed a Health Insurance Portability and Accountability Act of 1996 (HIPAA) compliant authorization statement. 2. Subject is at least 18 of age. 3. Subject has end stage renal disease (ESRD) adequately treated with thrice weekly dialysis. 4. Subject is currently stable on dialysis for at least 3 months on a conventional dialysis machine and Qd of 500ml/min or higher with no change in the following dialysis prescription parameters over that time: Qb, Qd, Dialyzer, Time. 5. Subject has a baseline Kt/V of greater than 1.2. 6. Subject has a stable vascular access. 7. Subject reports time to recovery of more than 4 hours or a modified ESAS with at least 5 symptoms of which at least 2 are rated as moderate (rating of 4-6) or severe (rating of 7-10).
Exclusion Criteria	
 1. Subject is unable to complete the questionnaires. 2. Subject is pregnant or planning to become pregnant. 3. Subject is scheduled for a change in modality or expected kidney transplant in the next 3 months. 4. Any other documented condition that the Investigator feels would prevent the Subject from successful inclusion in the study.
Primary Endpoint	Change in time to recovery and self-reported symptoms.
Secondary Endpoint	Caregiver assessment of changes in Subject's health, missed or reduced treatments, number of intradialytic interventions (saline, prn medications, early discontinuation, UF change related to sxS) and the reason for intervention.

2 ABBREVIATIONS

BUN	Blood Urea Nitrogen
CBC	Complete Blood Count
CFR	Code of Federal Regulations
CO2	Carbon Dioxide
QD	Dialysate Flow Rate
QB	Blood Flow Rate
ESRD	End Stage Renal Disease
ESAS	Modified Edmonton Symptoms Assessment System
FDA	Food and Drug Administration
GCP	Good Clinical Practice
HRQoL	Health Related Quality of Life
ICH	International Conference on Harmonization
KDQoL	Kidney Disease Quality of Life Survey
PHOS	Phosphorus
IRB	Institutional Review Board
K	Potassium
Na	Sodium
PI	Principle Investigator
TTR	Time to Recovery
UF	Ultrafiltration, volume of fluid removed

3 BACKGROUND

Subjects experience various symptoms during hemodialysis. Prior studies have shown that fatigue, muscle cramps, insomnia and pruritis are most commonly reported as symptoms associated with dialysis⁽⁵⁾. The frequency and severity of intradialytic symptoms are associated with missed treatments, shortened treatment time and delayed time to recovery after dialysis^(3,7,8). Longer time to recovery has also been shown to be a simple, reproducible, tool associated with poorer HRQoL, hospitalization and mortality^(3,4). Subjects treating on the Tablo system have previously reported feeling better when dialyzing thrice weekly with this device. The Tablo system utilizes a dialysate flow rate of 300ml/min to achieve the standard adequacy target as defined as a Kt/V of 1.2 or greater^(1,9). To better understand the feeling better effect on Tablo, this study was designed to determine if a decrease in dialysate flow rate on a conventional dialysis device produces a similar effect on Subject reported symptoms. This study assesses time to recovery as well as prevalence and severity of Subject reported symptoms via a weekly modified Edmonton Symptom Assessment System when dialysate flow rate is decreased from 500ml/min or higher

to 300ml/min on standard thrice weekly dialysis. In addition, the Subject's primary caregiver will be given a KDQoL SF-36 to complete as to their perception of the Subject's quality of life at baseline as well as after each 4-week interval. These assessment tools have been shown to be reliable, simple methods for symptom assessment (2,4,8,10,11,12)

4 STUDY OBJECTIVE

The objective of this study is to determine if Subjects who report dialysis symptoms while meeting adequacy (as determined by Kt/V of 1.2 or greater) on chronic thrice weekly dialysis or who have a recovery time of more than 4 hours when treated on a conventional, i.e. non Tablo, hemodialysis device feel better with a reduced dialysate flow rate of 300ml/min based on an assessment of time to recovery post dialysis, weekly modified ESAS, and Subject's caregiver assessment of the Subject's symptoms.

5 STATEMENT OF COMPLIANCE

This study will be conducted according to the protocol, good clinical practice (GCP) and all applicable regulatory requirements (21CFR).

6 STUDY DESIGN

This is a single center, post market, prospective, single blind, randomized, cross-over study involving approximately 50 subjects currently dialyzing on a conventional dialysis machine at a dialysate flow rate of 500ml/min or higher thrice weekly. The study may collect retrospective and prospective medical records and other treatment data. Enrolled subjects will answer the question, "How long does it take you to recover from a dialysis session?" (TTR) along with a modified ESAS at baseline and weekly. Subjects will be screened prior to entry into the study and enrolled if time to recovery at baseline of > 4 hours or the results of their modified ESAS demonstrate at least 5 dialysis related symptoms with at least 2 being described as moderate (rating of 4-6) or severe (rating of 7-10). Caregivers of screened Subjects meeting the study criteria will be given a baseline KDQoL SF-36 to determine their perception of the Subject's current state of health. Subjects enrolled will be randomized to two groups. Group 1 will dialyze for the first 4 weeks of the study at a Qd of 300ml/min, then for the last 4 weeks at a Qd of 500ml/min. Group 2 will dialyze for the first 4 weeks of the study at a Qd of 500ml/min, then for the last 4 weeks at a Qd of 300ml/min. At the end of each week, the Subject will respond to the TTR question as well as the modified ESAS survey. Subject caregivers will complete the KDQoL at the end of each 4-week interval. The study will assess the Subject and Subject caregiver responses to the survey tools as well as other outcome measures which may include but are not limited to, kinetics, laboratory values, blood pressure measurement, intradialytic interventions, missed or shortened treatments, and/or changes to treatment parameters. The study will collect subject demographics and dialysis related medications. The goal is to enroll at least 15 Subjects who report intradialytic symptoms as the ITT group for study analysis.

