6.3 Blinding and Randomization

This study is a single center, post market, prospective, single blind, randomized, cross-over study comparing symptoms with a conventional dialysis device at a Qd of 500 ml/min and a Qd of 300 ml/min. Only Subjects will be blinded to the dialysis device Qd.

Subjects will be randomized to either arm at a 1:1 ratio using excel's RANDBETWEEN function. Subjects will be randomly assigned a 0 or a 1. Subjects that are assigned '0' will go to Group 1, and subjects that are assigned '1' will go to Group 2.

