7.4 Inclusion Criteria

Subjects must meet **ALL** of the inclusion criteria to be enrolled in the study.

1. Subject has provided informed consent and has signed a Health Insurance Portability and Accountability Act of 1996 (HIPAA) compliant authorization statement.
2. Subject is at least 18 of age.
3. Subject has end stage renal disease (ESRD) adequately treated with thrice weekly dialysis.
4. Subject is currently stable on dialysis for at least 3months on an FMC 2008K machine and Qd of 500ml/min or higher with no change in the following dialysis prescription parameters over that time: Qb, Qd, Dialyzer, Time.
5. Subject has a baseline Kt/V of greater than 1.2.
6. Subject has a stable vascular access.
7. Subject reports time to recovery of more than 4 hours or a modified ESAS with at least 5 symptoms of which at least 2 are rated as moderate (rating of 4-6) or severe (rating of 7-10).

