8 STUDY PROCEDURES AND DATA COLLECTION

8.1 Baseline Evaluation

Subjects will be asked for their response to the TTR question and a modified ESAS. Subjects meeting the inclusion and exclusion criteria, will be consented and enrolled into the study. Enrollees will be randomized to treatment Group 1 or 2. Enrollee caregivers will be asked to complete a KDQoL SF-36 regarding their perception of the Subject's overall health. Additionally, historical dialysis treatment information including hemodialysis prescription and any recent changes, baseline laboratory values including kinetics, temperature, height, weight, body mass index, vascular access type, presence or absence of diabetes mellitus, hypotension, ejection fraction, arrhythmia, high blood pressure, and any other co-morbid conditions considered relevant may also be collected where available. Any subjects of child-bearing potential will be given a pregnancy test to confirm negative results. Those subjects will also be utilizing medically acceptable means of contraception during the study period. Demographic information will be collected including age, gender, ethnicity and race. Dialysis related medications, laboratory values, blood pressure readings taken before, during and after dialysis treatments and adverse event data may also be collected if available.

8.2 Group 1

Subjects will undergo staff administered dialysis treatment 3 times/week for 8 weeks In-Center with prescription adjustments as outlined in the Schedule of Events. Subjects will respond to the TTR question and modified ESAS at the completion of every week. Caregivers will be asked to respond to the KDQoL SF-36 during week 4 and week 8. Subjects Serum Potassium, BUN, CO₂, Phos, Na, Beta-2-Microglobulin, Vitamin B12 and Kt/V labs and treatment flowsheets will also be evaluated. Dialysis prescription changes, dialysis related medications, blood pressure readings taken before, during and after dialysis treatments and adverse event data may also be collected if available. Group 1 will dialyze for the first 4 weeks of the study at a Qd of 300ml/min, then for the last 4 weeks at a Qd of 500ml/min.

8.3 Group 2

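### Does the weekly recovery-time question need a stated recall period because Qd switches directly between periods?

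*Protocol*

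**What the plan says.** The synopsis gives the primary endpoint as "Change in time to recovery and self-reported symptoms". Section 6 fixes the wording of the TTR item, "How long does it take you to recover from a dialysis session", and its timing: "At the end of each week, the Subject will respond to the TTR question as well as the modified ESAS survey". Each subject therefore gives four answers per period and eight over the study, besides baseline.

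Group 1 has four weeks at 300 ml/min and "then for the last 4 weeks at a Qd of 500ml/min" (Sections 6 and 8.2). Group 2 has the reverse order. Appendix A places the switch between Week 4 and Week 5, with no week set aside. Before entry, Section 7.4 requires at least three months at 500 ml/min or higher with "no change in the following dialysis prescription parameters over that time: Qb, Qd, Dialyzer, Time".

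On what subjects know, Section 6.3 says "Only Subjects will be blinded to the dialysis device Qd". Section 7.2 requires that they be fully told the study's purpose and relevant details. Section 10 says they will be told that weekly Kt/V may fall because Qd is changed, and that symptoms may lessen.

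On the instruments, Section 3 says "These assessment tools have been shown to be reliable, simple methods for symptom assessment". Among the sources cited there is the methods paper on the recovery-time question (reference 4), whose title claims responsiveness to change as well as reliability and validity.

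**The concern.** The question is general and in the present tense, and it names neither a period nor a session. A subject with months of stable treatment could give a habitual answer. Qd changes from one week to the next, and Group 1 also changes at Week 1. If subjects did not realise that recent sessions might differ, the first answers after a switch would mix old and new Qd and pull the difference toward zero. In a small study (a goal of at least 15 subjects in the analysis group) a diluted difference could be read as no effect. An SAP can choose weeks, but it cannot add a recall period to answers already collected, so the wording would have to be settled beforehand.

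**Working it through.** The protocol states no figure on this point, so there is none to reproduce. The check has three parts.

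**1. How much could be lost, under an assumed recall length?**

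Inputs from the protocol: four weekly answers per period, two sequences in a 1:1 ratio, a direct switch. Assumed: each answer is the plain average of the last *w* weeks. Code 300 as 1, 500 as 0 and the pre-study level as *p*. Let *m* be the mean, over the weeks *k* used in a period, of min(*k*, *w*)/*w*. For *w* up to 4:

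- Group 1 difference: [*m* + *p*(1 − *m*)] − (1 − *m*) = 2*m* − 1 + *p*(1 − *m*)
- Group 2 difference: *m* − *p*(1 − *m*)
- Average of the two: (3*m* − 1)/2, with *p* cancelling

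All four weeks: *m* = 1, 0.875, 0.75, 0.625 for *w* = 1, 2, 3, 4. For *w* = 2 this gives (2.625 − 1)/2 = 0.8125.

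| Weeks used | *w* = 1 | *w* = 2 | *w* = 3 | *w* = 4 |
|---|---|---|---|---|
| All weeks | 100% | 81% | 63% | 44% |
| Weeks 3–4 vs 7–8 | 100% | 100% | 100% | 81% |
| Week 4 vs Week 8 | 100% | 100% | 100% | 100% |

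Only recall longer than a whole period defeats every choice of weeks. At an assumed 6 weeks the three rows become 15%, 38% and 50%.

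A milder assumption is that only the first answer after a switch is affected. If a quarter of that answer reflects the old Qd, *m* = 1 − 0.25/4 = 0.9375 and 91% is kept over all weeks. If half does, 81% is kept. Leaving out that first week restores 100%.

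The loss thus runs from nothing to large according to *w*, and the protocol gives no information on *w*. An equal-weight average over several weeks is a severe assumption for a present-tense question repeated at each week's end.

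**2. Are subjects unaware that recent sessions may differ?**

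Section 6.3 hides the current Qd. Sections 7.2 and 10 disclose that Qd is being changed and that symptoms may respond. Read together, subjects do not know which setting they are on, but they do know that treatment is being varied. Blinding therefore does not supply the reason for looking back past a switch.

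**3. Is restricting the analysis to late weeks a cheap safeguard?**

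If the precision cost is worked out from the within-period correlation *r* of weekly scores alone, the standard error rises by √{[(1 + (*n* − 1)*r*)/*n*] / [(1 + 3*r*)/4]} when *n* weeks replace four. At *r* = 0.7 that is 5% for *n* = 2 and 14% for *n* = 1. But the comparison is within subject, so the correlation *b* between scores in different periods must be subtracted from numerator and denominator:

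√{[(1 + (*n* − 1)*r*)/*n* − *b*] / [(1 + 3*r*)/4 − *b*]}

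- *r* = 0.7, *b* = 0.5 (assumed): *n* = 2 gives √(0.35/0.275) = 1.13; *n* = 1 gives √(0.50/0.275) = 1.35.
- *r* = 0.5, *b* = 0.4 (assumed): *n* = 2 gives √(0.35/0.225) = 1.25; *n* = 1 gives √(0.60/0.225) = 1.63.

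Late weeks protect against recall lag at a real price in precision. Weighing the two is an analysis decision, which a protocol may leave to the SAP.

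**The case for a change.** The strongest case for acting is that a lead-in is one line on one form, that it concerns a primary endpoint, and that it cannot be added afterwards. Asking every week fixes how often the subject answers, not the period the answer covers. Part of this stands: the wording quoted in Section 6 has no recall period, the switch is direct, any lag of this kind would weaken the difference, and no analysis can change how a question was asked.

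The step from there to a defect does not stand. A past-week reading is at least as natural and costs nothing. The worksheets mentioned in Section 12 are not shown and may already carry a lead-in. Nor is the change free. It departs from the form of an item chosen for its published performance. It alters the baseline question behind the eligibility rule "Subject reports time to recovery of more than 4 hours or a modified ESAS with at least 5 symptoms", although the threshold and the stable pre-study Qd make that effect small. It would also weaken comparison with earlier studies, which Section 11 leaves open, as far as that covers TTR. It would do nothing about any physical carryover.

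**Conclusion.** No error. The missing recall period and the direct switch are facts of the protocol, but harm follows only if answers average more than one week, and nothing in the document shows that they do. If they did, the difference kept would be 81% to 44% over all weeks for recall of 2 to 4 weeks, and 100% for Week 4 against Week 8. These percentages rest on an assumed equal-weight recall and equal-sized sequences, so they show what could happen and are not estimates. Subjects are told that Qd is varied, the item is used in its established form, and four answers per period leave the SAP room to choose its weeks. Whether to add a lead-in is a trade-off on which reasonable statisticians would differ.

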6.1 Effort to Minimize Bias

All eligible Subjects that, in the treating physician's best medical judgement, meet the selection criteria will be asked to participate in this study. Subjects will not be excluded based on gender, race, ethnicity or sexual orientation.

6.2 Evaluation of Safety

Treatment with a Qd of 300ml/min has been shown to be safe and effective in the treatment of ESRD subjects. It has also been demonstrated that dialysis at a Qd of 300ml/min can achieve the prescribed adequacy target of a Kt/v of 1.2 or greater. Standard safety precautions as per clinic protocol will be continued. No portion of this study will be beyond the standard of care.

6.3 Blinding and Randomization

This study is a single center, post market, prospective, single blind, randomized, cross-over study comparing symptoms with a conventional dialysis device at a Qd of 500 ml/min and a Qd of 300 ml/min. Only Subjects will be blinded to the dialysis device Qd.

Subjects will be randomized to either arm at a 1:1 ratio using excel's RANDBETWEEN function. Subjects will be randomly assigned a 0 or a 1. Subjects that are assigned '0' will go to Group 1, and subjects that are assigned '1' will go to Group 2.

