Subjects will undergo staff administered dialysis treatment 3 times/week for 8 weeks In-Center with prescription adjustment as outlined in the Schedule of Events. Subjects will respond to the TTR question and modified ESAS at the completion of every week. Caregivers will be asked to respond to the KDQoL SF-36 during week 4 and week 8. Subjects Serum Potassium, BUN, CO₂, Phos, Na, Beta-2-Microglobulin, Vitamin B12 and Kt/V labs and treatment flowsheets will also be evaluated. Dialysis prescription changes, dialysis related medications, blood pressure readings taken before, during and after dialysis treatments and adverse event data may also be collected if available. Group 2 will dialyze for the first 4 weeks of the study at a Qd of 500ml/min, then for the last 4 weeks at a Qd of 300ml/min.

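### The Qd blind covers subjects only, so the caregivers whose Week 4 and Week 8 ratings form a secondary measure are outside it

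*Protocol*

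**What the plan says.** Section 6.3 describes a single-blind crossover of Qd 500 against Qd 300 and sets the extent of the blind: "Only Subjects will be blinded to the dialysis device Qd".

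Subjects are not the only people who complete questionnaires:

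- The synopsis opens its list of secondary measures with "Caregiver assessment of changes in" the subject's health.
- Section 4 includes the caregiver's assessment among the three assessments by which it judges whether subjects feel better.
- Section 3 makes clear that the rating is a perception: the "primary caregiver will be given a KDQoL SF-36 to complete as to their perception of the" subject's quality of life.
- Section 6 sets the timing: "Subject caregivers will complete the KDQoL at the end of each 4-week interval". Sections 8.2 and 8.3 repeat it for both groups: "Caregivers will be asked to respond to the KDQoL SF-36 during week 4 and week 8".

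Section 8.2 has staff deliver the treatment: "Subjects will undergo staff administered dialysis treatment 3 times/week for 8 weeks In-Center with prescription adjustments". Section 8.3 says the same for Group 2. The Qd switch falls between Weeks 4 and 5 in both groups (Appendix A).

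The primary endpoint, "Change in time to recovery and self-reported symptoms", comes from the blinded subjects.

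**The concern.** A caregiver's view of someone else's quality of life is a subjective outcome, and such outcomes are open to the rater's expectations. The protocol protects one set of raters from knowing the Qd and, by its wording, leaves the other set unprotected. Section 6.1 is headed as the effort to minimize bias but deals only with who is invited. Section 9 lists limitations without mentioning caregiver ratings made without a blind.

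The Week 4 and Week 8 ratings are the only caregiver ratings made under the assigned Qd, so they carry the whole caregiver comparison of 300 with 500. If knowledge of the Qd moves them, the descriptive difference that Section 11 allows for would mix the effect of Qd with the effect of knowing it. The direction cannot be predicted. Section 10 has subjects told both of a possible reduction in symptoms and of a possible fall in weekly Kt/V, and nothing says what caregivers are told.

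**Working it through.** The protocol gives no figure to reproduce here. The check has two parts.

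**1. Reading the text.** I looked for anything that would keep Qd from caregivers.

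| Place | What it covers | Masks caregivers? |
|---|---|---|
| Section 6.1 | Who is asked to take part | No |
| Section 6.3 | Limits the blind to subjects | No, excludes them by its wording |
| Sections 8.2, 8.3 | Staff-delivered dialysis; caregiver KDQoL at Weeks 4 and 8 | No |
| Section 13 | General training on study requirements | Not mentioned |
| Appendix A | Qd by week and rating weeks | No |

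**2. Does the crossover remove the bias?** Let:

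- tau = true Qd effect on the caregiver rating (300 minus 500)
- pi = period effect (period 2 minus period 1)
- p = share of caregivers who know the Qd
- d = shift in the 300-minus-500 difference among those caregivers, sign open

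Expected differences, 300 minus 500:

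- Group 1 (300 then 500): W4 - W8 = tau - pi + p·d
- Group 2 (500 then 300): W8 - W4 = tau + pi + p·d
- Mean of the two groups: tau + p·d

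The period effect cancels and p·d does not. If p and d differ by group, the bias is the average of the two products, (p1·d1 + p2·d2)/2. Adjusting for baseline B changes nothing, since (W4 - B) - (W8 - B) = W4 - W8.

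**Size.** The protocol gives neither p nor d. I assume |d| from 0.2 to 0.5, in SDs of the within-subject difference, and p from 0 to 0.5.

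| p | \|d\| = 0.2 | \|d\| = 0.5 |
|---|---|---|
| 0 | 0 | 0 |
| 0.25 | ±0.05 | ±0.125 |
| 0.5 | ±0.10 | ±0.25 |

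The yardstick is the standard error of the mean of the two group means, in the same units: sqrt((1/n1 + 1/n2)/4). Section 6 gives a goal of at least 15 subjects and an approximate total of 50. The splits are my assumption.

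- 15 subjects, 7/8: sqrt((1/7 + 1/8)/4) = 0.259
- 50 subjects, 25/25: sqrt((1/25 + 1/25)/4) = 0.141

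At 15 subjects the largest bias considered, 0.25, stays below one standard error. At 50 the bias passes one standard error when p exceeds 0.1414/0.5 = 0.28 with |d| = 0.5. With |d| = 0.2 it would need p above 0.1414/0.2 = 0.71, which is outside the assumed range.

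**The case against.** The strongest reply is that no exposure is documented. The sentence in Section 6.3 can be read as restating that the trial is single blind. The protocol does not say caregivers will be told the Qd, gives them no part in treatment, and has them rating a person who is blinded. Both p and d are assumed, the range includes zero, and most of it lies below one standard error. The 7/8 and 25/25 splits are also assumed, since assigning each subject by an independent random 0 or 1 does not guarantee balance. The measure is one of several secondary ones, the only analysis named is descriptive, and no decision rule depends on it. Finally, staff who know the Qd deliver the intradialytic interventions counted among the same secondary measures. That exposure follows from the text, and masking caregivers would not touch it.

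Most of this stands as a limit on weight. The bias is possible, not shown, and an uneven split would only raise the standard error. It does not answer the point itself. Staff have to know the Qd in order to set it, but no passage gives caregivers such a need. The protocol neither prevents disclosure nor provides for recording it, so a reader of the results could not tell whether it happened. A descriptive difference carries the same bias as a tested one. The staff exposure is a separate matter and no reason to leave this one open.

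**Conclusion.** The concern holds. The protocol sets a blind that leaves out the raters of one of its own secondary measures, and nothing else in it protects those ratings.

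The consequence is confined to the caregiver KDQoL contrast at Weeks 4 and 8. Its size cannot be derived from the protocol. On the assumed range it runs from none to 0.25 SD of the within-subject difference, in either direction. That is at most about one standard error with 15 subjects (0.25 against 0.259) and up to 0.25/0.141 = 1.8 standard errors with 50.

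This should be corrected because it is cheap and improves how the measure can be read. It does not threaten the trial's main comparison. My confidence is medium, because whether any caregiver would learn the Qd is unknown.

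**What to change.** - **Section 6.3:** state that both subjects and their caregivers are blinded to Qd and to sequence.
- **Section 13:** add to the training that staff do not disclose Qd to either.
- **Failed masking:** where the blind cannot be kept for a caregiver, record this and report that rating as unblinded.
- **If the sponsor keeps the present blind:** say in the protocol that the caregiver ratings are unblinded, and interpret them accordingly.

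The cost is one sentence, one item in training that is already required, and a short record of any failed masking. Staff would withhold Qd from one more person per subject, so 15 to 50 people. Caregiver is not defined, so some may have a reason to know the Qd. The unblinded label is meant for them.

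A separate clerical point, given no weight above, can be settled in the same amendment. The baseline caregiver KDQoL is assigned to caregivers of screened subjects in Section 6, to caregivers of enrollees in Section 8.1, and to Week -1 in Appendix A, ahead of consent at Week 0. The baseline modified ESAS and TTR row is also at Week -1. These passages should be reconciled on who completes the forms and when relative to consent. The timing does not affect the Qd contrast.

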7.5 Exclusion Criteria

If **ANY** of the exclusion criteria are met, the Subject is excluded from the study.

1. Subject is unable to complete the questionnaires.
2. Subject is pregnant or planning to become pregnant
3. Subject is scheduled for a change in modality or expected kidney transplant in the next 3 months.
4. Any other documented condition that the Investigator feels would prevent the Subject from successful inclusion in the study.

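### Section 6.3 allocates by Excel's RANDBETWEEN and requires no fixed, concealed, independently held or logged list, although only subjects are blinded

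*Protocol*

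**What the plan says.** Protocol section 6.3 names the tool and the ratio: "Subjects will be randomized to either arm at a 1:1 ratio using excel's RANDBETWEEN function". It then gives the form of the draw, "Subjects will be randomly assigned a 0 or a 1", and its mapping: "Subjects that are assigned '0' will go to Group 1, and subjects that are assigned '1' will go to Group 2". The same section limits the blind: "Only Subjects will be blinded to the dialysis device Qd".

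Section 8.1 gives the timing. Baseline recovery time and symptoms are collected, eligible subjects consent and are enrolled, and then "Enrollees will be randomized to treatment Group 1 or 2".

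Section 6 describes a single-center "cross-over study involving approximately 50 subjects currently dialyzing on a conventional dialysis machine". Group 1 has Qd 300 in the first four weeks and Qd 500 in the second four; Group 2 has the reverse. The same section sets a floor: "The goal is to enroll at least 15 Subjects who report intradialytic symptoms as the ITT group for study analysis".

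The protocol does not say who makes the draw or where, whether it is made in advance or subject by subject, or whether the result is frozen, dated, concealed or logged.

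**The concern.** RANDBETWEEN has no seed argument and recalculates. That is a general property of the function, not something the protocol states. A list drawn with it cannot be reproduced later, so the only proof of the allocation is a saved copy, and the protocol asks for none. With everyone but the subject open to the flow rate, and baseline symptoms known before the draw, the text leaves room for a draw to be repeated without trace.

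Sequence is the only thing this design randomizes, and it is what separates the Qd effect from change over time. Subjects enter because they have a long recovery time or a high symptom burden, so drift over eight weeks is plausible. If subjects expected to improve were placed in Group 2, which has Qd 300 second, their improvement would be credited to Qd 300. If no list was saved, there would be no means of showing that this did not happen.

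**Working it through.** The protocol gives no sample-size calculation, SD, alpha or power, so there is no figure of its own to reproduce. The check is of the text first, and then of scale.

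**1. Does another section supply the protection?**
- Section 6.1, on minimizing bias, covers who is invited and non-discrimination. It does not mention allocation.
- Section 8.1 places the draw after consent, eligibility and enrollment. It names no person, place or record.
- Section 12 requires essential documents to be retained. It names no allocation list or log.
- Appendix A has rows for consent and enrollment but none for randomization.

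None of them requires the draw to be fixed, concealed, independently held or logged.

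**2. How easily would a redraw reach a preferred group?** Each draw is 0 or 1 with probability 0.5 (section 6.3). Within k draws the preferred value appears with probability 1 − 0.5^k: 50% for k = 1, 75% for k = 2, 87.5% for k = 3. This shows what is possible, not that it would occur.

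**3. Size of the bias under deliberate steering.**
- Contrast: half the difference between Group 2 and Group 1 in mean Period 2 minus Period 1 change. The protocol names no estimator (section 11 gives descriptive statistics only); this usual cross-over contrast is used for scale.
- q: fraction of subjects steered, assumed 0.2 to 0.5.
- ρ: correlation between the guess that drives the steering and the subject's own time trend, assumed 0.3 to 0.5.
- SD: standard deviation of the within-subject period difference. It is not given, so results are in SD units.

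If steered subjects with an above-average guess go to one group and the rest to the other, and the guess is normally distributed, their mean trends differ by 2 × ρ × √(2/π) × SD. Halving this and weighting by q gives:

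bias = q × ρ × √(2/π) × SD = q × ρ × 0.798 SD

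**4. Standard error of the same contrast.** With equal groups, SE = ½ × SD × √(2/n + 2/n) = SD/√n. This is 1/√50 = 0.141 SD at about 50 subjects and 1/√15 = 0.258 SD at the floor of 15 (an 8:7 split gives 0.259).

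| q | ρ | Bias (SD) | Bias ÷ SE, n = 50 | Bias ÷ SE, n = 15 |
|---|---|---|---|---|
| 0.2 | 0.3 | 0.048 | 0.34 | 0.19 |
| 0.2 | 0.5 | 0.080 | 0.56 | 0.31 |
| 0.5 | 0.3 | 0.120 | 0.85 | 0.46 |
| 0.5 | 0.5 | 0.199 | 1.41 | 0.77 |

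At 50 subjects only the most pessimistic corner exceeds one standard error. At 15 none does.

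**The case against.** The strongest reply is that the protocol may be followed soundly as it stands. The values could be drawn once, pasted as fixed values and held by the sponsor, and a randomization plan or SAP that is not shown may say so. This stands as far as it goes. A reader might infer that the formula stays live in a worksheet at the clinic, or that the allocation can never be verified. The text supports neither: it does not say who runs the draw, and saved values would allow verification. An accidental recalculation would also do no harm by itself, since it gives another equally random list. Bias needs someone to redraw selectively.

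A reader might also see the discretionary exclusion in section 7.5 as a route to steering. Section 8.1 puts eligibility before randomization, so that route needs advance knowledge of the next assignment, which the text does not indicate.

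Three further points limit the consequence. Every subject receives both flow rates, so steering cannot decide who gets Qd 300. Staff would have to predict an individual's trend over eight weeks. And the sequence actually given can be reconstructed from flowsheets and treatment records, although these do not show what was first drawn.

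Finally, a seed alone does not stop anyone from trying several seeds; the protection comes mainly from custody and the log. That is right, and it shapes the fix.

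What the reply does not remove is that the protocol itself chose the tool. A recalculating function without a seed is poorly suited to an auditable list, and no other section compensates for it.

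**Conclusion.** The point holds in a limited form. Section 6.3 fixes an unseeded, recalculating function as the allocation method and requires no frozen and dated list, concealment, independent holder or release log, while only subjects are blinded. The sequence cannot be regenerated, and an unrecorded redraw for a given subject is compatible with the text.

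The size is conditional: about 0.05 to 0.20 SD of the within-subject period difference, against a standard error of 0.14 SD (n = 50) or 0.26 SD (n = 15). It rests on assumed deliberate steering of 20% to 50% of subjects, an assumed correlation of 0.3 to 0.5 with the time trend, and the usual cross-over contrast. None of these comes from the protocol, and nothing in it suggests that steering is intended or likely. The harm is confined to the order of treatment, and so to confounding of the Qd comparison with time trends. The change is still worth making: it is cheap beforehand, and a missing allocation record cannot be recreated once enrollment is over.

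**What to change.** In section 6.3, replace the RANDBETWEEN sentence with a short paragraph to this effect:

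- One allocation list is generated before the first enrollment by a seeded program and stored as fixed, dated values together with the program and seed.
- The list is held by an existing sponsor or study person who does not enrol or treat subjects.
- Each assignment is released only after the enrollment step of section 8.1 has been recorded for that subject.
- The list and the release log are kept in the study file.

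The cost is a one-paragraph amendment and about an hour of work. The downside is that the site must request each assignment instead of drawing it directly.
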